6.5 Blinding and Allocation/Randomization

At Visit 1, participants who fulfill all the inclusion criteria and none of the exclusion criteria will be assigned a unique randomization number in ascending numerical order at each study site. The randomization number encodes the participant's assignment to one of the two arms of the study according to the randomization schedule generated prior to the study. These randomization numbers are linked to the two treatment arms, which in turn are linked to container (kit) numbers. A separate container list will be produced. Subjects will be randomized

GlaxoSmithKline Consumer Healthcare Confidential Template Version Effective: 18-May-18 (CCR #11475) Page **29** of **64**

Diclofenac Diethylamine 2.32% Study 211206 Protocol Amendment 1

using an interactive response technology system and container numbers will be provided by the system.

Subjects will be randomized in a 1:1 ratio, with equal numbers receiving DDEA 2.32% + Placebo gel and DDEA 1.16% gel. Randomization numbers will be assigned to individual centers in order to stratify the randomization by center.

Before the study is initiated, training, login information and directions for the IRT will be provided to each site. Study products will be dispensed according to the instruction received through the IRT at the appropriate study visits.

Returned study products should not be re-dispensed to any subject.

The investigator's knowledge of the product allocation should not influence the decision to enroll a particular subject or affect the order in which subjects are enrolled.

This study is described as double-blind (the subjects and clinical examiner will be blinded to the product received). The study statistician, data management staff, other employees of the Sponsor and vendors acting on behalf of the sponsor, who may influence study outcomes will also be blinded to the product allocation. The placebo gel and active gels will be identical in packaging, labeling, odor, schedule of administration, and as identical as possible in appearance.

To ensure the examiner remains blinded throughout the study, staff involved in the preparation, dispensing, and application of study products will work in a separate area. The examiner is not permitted in any area where study product is stored, dispensed, or in use.

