12.2.6 Secondary Analysis(es)

Secondary outcome measures (endpoints) include:

- Change from baseline of POM on VAS on Days 3 and 8 respectively
- Tenderness measured by pressure algometry on Days 3, 5 and 8 (change from baseline and difference between the measurement in injured area and contralateral area)
- Change from baseline Ankle Joint Function (Karlsson Scoring Scale) on Days 3, 5 and 8
- Circumference measurement of swelling (change from baseline in circumference of affected ankle and comparison to non- affected ankle by Figure of Eight method on Days 3, 5 and 8)
- Pain Intensity and Pain Relief
 - Sum of Pain Intensity Difference (SPID) From hours 0 24 post first dose (corresponding to Day 1) and from hours 96 120 post first dose (corresponding to Day 5)
 - Total Pain Relief (TOTPAR) From hours 0 24 post first dose (corresponding to Day 1) and from hours 96 120 post first dose (corresponding to Day 5)

TOTPAR and SPID will be calculated as weighted sums of the Pain Relief Score and Pain Intensity Difference at each timepoint respectively:

 $TOTPAR = \Sigma R_t^x (time_t - time_{t-1})$

Where R_t = the pain relief score at time t and time t = time in hours post first dose

 $SPID_t = \Sigma PID_t (time_t - time_{t-1})(h)$

Where PI is pain intensity

- Use of rescue medication, for ankle sprain and overall
 - Total number of tablets used
 - Total number of days on which rescue medication was used

Figures will show the time course of outcomes by treatment group for key quantitative outcomes.

For POM, Karlsson score, tenderness, swelling and diary assessments (SPID and TOTPAR), an ANCOVA model including treatment group and center as main effects, and the baseline value as covariate (those outcomes for which there is a baseline) will be used for analysis, with the treatment difference and 95% confidence interval (two-sided) presented for each assessment.

Use of rescue medication (number of tablets and days used) will be compared between treatments using the CHM method (modridit scores) stratified by center, with the median treatment differences and 95% confidence intervals (2-sided) presented using Hodges-Lehmann estimation.

These secondary endpoints will be analyzed using the per protocol and mITT populations.

GlaxoSmithKline Consumer Healthcare Confidential Template Version Effective: 18-May-18 (CCR #11475) Page **54** of **64**

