## 4.1 Subgroups/Stratifications

Center/Site will be used as stratification factor where ever it is required. Based on study requirement sub group analyis will be conducted.

GlaxoSmithKline Consumer Healthcare Confidential

Page 10 of 36

211206

Statistical Reporting and Analysis plan Draft V2.0 20JAN2021

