#### 4.4.3 Rescue Medication

The investigator will provide rescue medication (paracetamol 500mg tablets) to the subjects at the baseline visit. Rescue medication will be re-dispensed on Day 5 i.e.at Visit 3. Subjects are not allowed to take rescue medication within 6 hours of study visits and within 12hours of Day 5. Following information will be documented in the Rescue Medication CRF page –

- Rescue medication taken (yes/no) (RMYN)
- Pain intensity (RMPI) and pain relief (RMPR) before taking rescue medication
- Reason for use of rescue medication (RMREAS)
- Time (RMSTTM) and date (RMSTDTC) of rescue medication
- Number of tablets taken (RMNUM)

Summuary of all the above mentioned points will be displayed in PPD . and will be listed in PPD .

Time to first use of rescue medication will be analyzed using the survival estimate of median time to event for each treatment group along with the CI for median. P-value from Log Rank test will be used to compare the median times between the treatment groups (**PPD**).

Kaplan Meier plot will be presented for the survival probabilities against the time points for both the treatment groups (In case number of events are considerable).

Subjects with no use of rescue medication will be censored at their last available date in the study.

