## 5 Changes to the Protocol Defined Statistical Analysis Plan

- 1. Rescue medication analysis has been performed considering time to event data. Whereas, protocol planned "Hodge Lehmann" analysis has not been performed.
- 2. For Pain Intensity and Pain Relief, as per protocol for Day 1 it is "Sum of 0-24 hrs" and "Sum of 96-120 hrs". Based on discussion and time consideration Day 5 will also be displayed as "Sum 0-24 hours".

GlaxoSmithKline Consumer Healthcare Confidential

Page 27 of 36

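### The SAP compares time to first rescue use only by a log-rank p-value described as comparing medians, with no center stratification specified and no between-arm estimate or interval

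*SAP*

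**What the plan says.** Protocol 12.2.6 compares the number of rescue tablets and the number of days of use between arms "using the CHM method (modridit scores) stratified by center, with the median treatment differences and 95% confidence intervals (2-sided) presented using Hodges-Lehmann estimation". Protocol 6.5 adds: "Randomization numbers will be assigned to individual centers in order to stratify the randomization by center".

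SAP section 5 changes this: "Rescue medication analysis has been performed considering time to event data". It also records that the Hodges-Lehmann analysis is not done. The replacement in SAP 4.4.3 is time to first rescue use, reported as the "survival estimate of median time to event for each treatment group along with the CI for median". The only comparison between arms is then: "P-value from Log Rank test will be used to compare the median times between the treatment groups". A Kaplan-Meier plot follows only if there are enough events. The censoring rule after 4.4.3 counts time in whole calendar days from randomization.

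SAP 1.2 still lists tablets and days of use, for ankle pain and overall, as endpoints. The secondary efficacy analyses in SAP 4.5.2 and 4.6.1 do not include them. On stratification in general, SAP 4.1 says: "Center/Site will be used as stratification factor where ever it is required".

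**The concern.** Three things are missing or misdescribed.

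- **No effect estimate.** Two separate medians and a p-value do not show how large a difference in rescue use could be. The protocol's plan did give a difference with an interval. The reason in SAP section 5, that time-to-event data allow a clear analysis, does not explain why the interval was given up.
- **Wrong description of the test.** The log-rank test compares whole event-time distributions. It can reject when the medians are equal, and it can be computed when neither median exists.
- **Center is not addressed.** Randomization and the protocol's rescue test are stratified by center, but 4.4.3 does not say whether the log-rank test is.

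Rescue use matters for reading a non-inferiority result, because more paracetamol in the DDEA 2.32% arm could partly hide a weaker gel. A non-significant p-value with no interval cannot rule out a meaningful imbalance.

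**Working it through.** **The plan's own figure.** The documents give no power figure for rescue use. Their only one is for the primary endpoint (Protocol 12.1: SD 22 mm, true difference 5 mm, margin 13 mm, 80% power, two-sided 95% CI), and it reproduces: n = 2 × (1.960 + 0.842)² × 22² / (13 − 5)² = 118.7, so 119 per arm against the stated 120. Power at 120 per arm is 80.4%.

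**Can a median be reached?** A Kaplan-Meier median exists only if the curve falls to 0.5. The documents give no rescue rate, so two values are assumed, with an assumed hazard ratio of 0.65:

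- 30% of the higher-use arm rescued in 7 days: the curve ends at 0.70, so neither arm has a median.
- 60% rescued: the curve ends at 0.40, so that arm has a median. The other arm ends at 0.40^0.65 = 0.55, so it has none.

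Whether a median exists therefore depends on the unknown rescue rate.

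**What would an unstratified test cost?** At each event day the log-rank test adds d₁ − d·n₁/n to U and d(n₁/n)(1 − n₁/n)(n − d)/(n − 1) to V, and Z = U/√V. Here d is the number of events, n the number at risk, and subscript 1 marks one arm. The stratified version computes these within each center and then sums them.

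Inputs from the documents: about 300 subjects, 1:1 within center, at least 8 centers (300/40 = 7.5), about 7 days of treatment, whole-day times. Assumed inputs: hazard ratio 0.65, rescue use of 30% or 60% in the higher-use arm at an average center, 8 to 30 equal centers, and the SD of center log-hazards. There were 800 runs per cell at two-sided 5%. The Monte Carlo standard error of one power value is at most √(0.25/800) = 1.8 points.

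Power in %, unstratified / stratified:

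| Centers | Use | SD 0 | SD 0.5 | SD 1.0 |
|---|---|---|---|---|
| 8 | 30% | 46.9 / 46.9 | 46.1 / 46.9 | 40.0 / 52.2 |
| 8 | 60% | 75.0 / 75.4 | 72.8 / 76.5 | 60.4 / 78.4 |
| 10 | 30% | 47.4 / 46.9 | 45.5 / 47.6 | 41.4 / 54.2 |
| 10 | 60% | 78.7 / 77.9 | 72.9 / 78.5 | 53.4 / 71.8 |
| 20 | 30% | 46.4 / 45.0 | 45.0 / 47.5 | 40.7 / 54.1 |
| 20 | 60% | 77.7 / 77.1 | 69.5 / 74.0 | 54.6 / 73.8 |
| 30 | 30% | 48.6 / 47.9 | 43.5 / 46.4 | 40.9 / 52.4 |
| 30 | 60% | 78.1 / 74.5 | 71.8 / 74.1 | 55.1 / 74.1 |

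The gain from stratifying is −3.6 to +0.4 points at SD 0, +0.8 to +5.6 at SD 0.5, and +11.5 to +19.2 at SD 1.0.

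With no treatment effect (2,000 runs per cell, 10 or 20 centers), the unstratified test rejects in 4.1% to 4.2% at SD 0.5 and in 1.8% at SD 1.0. The stratified test rejects in 4.7% to 5.9%. The standard error at 5% is √(0.05 × 0.95/2000) = 0.5 points.

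A second simulation (10 centers, hazard ratio 1.6, about 40–45% using rescue in 8 days, 1,500 trials per scenario) agrees. Unstratified against stratified power was 73/72, 71/74 and 58/75% at SD 0, 0.5 and 1.0.

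**The case against.** Several stronger readings are tempting, and the documents do not support them.

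- **That the test is unstratified.** SAP 4.4.3 is silent. SAP 4.1 leaves room for center strata wherever they are required, and the code under the rescue heading in Appendix 4 is not shown in the public text. Elsewhere the SAP names center when it means to use it, as in the primary ANCOVA, the Van Elteren fallback and the secondary ANCOVA. That makes the omission notable but does not settle it. What stands is that stratification is not specified.
- **That power is lost.** Any loss depends on how much centers differ in rescue use, and the documents give no figure for this. At SD 1.0, centers one SD above and below average differ e² = 7.4-fold in hazard, which is a strong assumption. Without center differences, stratifying over many small centers can itself cost a few points.
- **That the median will not be reached.** This follows from whatever rescue rate is assumed. It is a possibility, not a prediction.
- **That first use for headache or fever counts as an event.** Protocol 6.10 allows rescue for such reasons, but SAP 4.4.3 does not define which reasons qualify. It does summarize the reason for use, and SAP 1.2 keeps ankle-pain and overall use apart. The definition is unspecified, not shown to be wrong.
- **That the protocol's stratified test is withdrawn.** SAP section 5 expressly drops only the Hodges-Lehmann analysis. However, no SAP section schedules the stratified comparison of tablets and days.
- **That the trial's conclusion is at risk.** Rescue use is secondary, and success rests on Day 5 pain on movement alone. Rescue is also barred for 12 hours before Visit 3, which limits masking without excluding it. Nothing in the documents says that a non-significant rescue result will be read as no difference.

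None of this supplies the missing between-arm estimate or makes a log-rank test a comparison of medians.

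**Conclusion.** The point holds in limited form. As written, the SAP's inferential comparison of rescue use is a single p-value, misdescribed as comparing medians, with center unspecified and the protocol's interval dropped. That follows from the text and needs no simulation.

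The power cost is conditional on the test being run unstratified. It is about nil if centers do not differ, about 1 to 6 points at a center log-hazard SD of 0.5, and about 11 to 19 points at SD 1.0. The hazard ratio, rescue rates and SDs behind these figures are assumptions. The error is in the conservative direction. This is a worthwhile improvement to a secondary analysis that helps in interpreting the primary result, and does not change it.

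**What to change.** Amend SAP 4.4.3 and section 5 before unblinding:

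1. Specify the log-rank test as stratified by center, and describe it as a comparison of time-to-event distributions.
2. Add a hazard ratio with 95% CI from a Cox model stratified by center, naming a tie method suited to whole-day times (for example Efron or exact).
3. Report Kaplan-Meier percentages rescued by fixed days within common follow-up, with the between-arm difference and CI. Days 3 and 5 qualify. The last should be no later than Day 7, because the final visit is Day 8 ± 1.
4. Define the event, and present ankle-pain and overall use separately using the collected reason (RMREAS).
5. Keep the protocol's center-stratified comparison of tablets and days, with its Hodges-Lehmann differences and CIs, because SAP 1.2 still lists these endpoints.

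The cost is SAP wording and a few extra outputs from data already collected. If there are many small centers that do not differ, stratifying may give up a few points of power (3.6 in the worst simulated case, 30 centers of 10).

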#### **Censoring Rule:**

GlaxoSmithKline Consumer Healthcare Confidential

Page 18 of 36

Event : If event occurred then value of censor is 0, time will be derived as follows: Date of First Occurrence of Event- Date of Randomization + 1

Censor: If event not occurred then value of censor is 1, time will be derived as follows: Last Available Date in the study - Date of Randomization + 1

Where, Last Available Date in the study = Maximum of (Date of Discontinuation, Date of Death, Date of Follow-up, Study Completion Date)

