6.2 Administration

All subjects will be given 4 tubes of study drug and the same usage instructions. Subjects should spread a total of approximately 2 grams of study medication (using the dosing card) on both sides of the ankle. The study drug should be applied topically with the fingertips to both sides of the affected ankle for approximately 1 minute (corresponds to a region of approximately 200 cm²). After application, the hands should be washed. On Day 1, to demonstrate proper application, the first dose of study drug will be applied at the study center from the morning tube (regardless of the time of randomization). Subsequent doses will be applied from the tube associated with the corresponding time of day separated by at least 3 hours (i.e. if the first dose is applied at 15:00 hr from the morning tube, the next dose will be at approximately 18:00 hr from the late afternoon tube and the next dose will be applied on Day 1, if possible, preferably with at least 3 hours between doses.

The subjects will be instructed to continue to apply the gel topically with the fingertips four times a day for 7 days. Dosing times should be distributed as evenly as possible over the day, preferably once upon first arising (i.e., after washing or shower or bath), once at lunch (approximately 12:00 hour), once in the late afternoon (approximately 17:00 hour), and once in the late evening (i.e., after washing approximately 21:00 hour). There should be a period of at least 4 hours between individual applications. The appropriately-labeled tube should be used for each application.

Subjects can take a shower or bathe prior to application. Subjects should not shower, bathe or wash the treated area within the first three hours after the application. Subjects should wash their hands after use and should wait 10 minutes before covering the treated skin with clothing.

The investigator will instruct the subject to take the study drug exactly as prescribed and state that compliance is necessary for the subject's safety and the validity of the study. The subject will be told to contact the investigator if he/she is unable for any reason to take the gel as directed/prescribed. All dosages prescribed and dispensed to the subject and all dose changes during the study must be recorded on the Dosage Administration Record CRF. Any missed or skipped doses must be recorded in CRF.

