6.8 Subject Diary

A diary will be handed out to the subject at Visit 1, Visit 2, and Visit 3.

- Every time gel is applied, the subject must document the time and date of application. This includes gel applied at the clinic site
- Pain intensity and pain relief will both be assessed by the subjects every 2 hours ± 30 minutes (after starting study drug) until the subject goes to bed on the evening of Day 1. The same assessment and recording frequency will also be followed starting with the first dose on Day 5. On Day 1 and Day 5 where an assessment time point coincides with a dosing time point, the assessment of pain intensity and pain relief should be made prior to the dose. For all other time periods, pain intensity and pain relief will be assessed and recorded immediately prior to each study drug application.
- Every time rescue medication is taken (not allowed within 6 hours of Study Visits and within 12 hours of Study Visit 3), the subject must document:
 - Time and date of rescue medication
 - Number of tablets taken
 - Reason for use of rescue medication
 - $\circ\,$ Pain intensity and pain relief immediately prior to each dose of rescue medication

The Investigator or designee will ensure that all diary entries completed by the subject are legible. The Investigator will review the diary at each clinic visit. The diary handed out to subjects on Visit 1, Visit 2, and Visit 3 will be collected by the Investigator or designee at Visit 2, Visit 3, and Visit 4 (Day 8±1) respectively.

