6.10 Rescue Medication

The investigator will provide rescue medication (paracetamol, 500 mg tablets) to the subject at the baseline visit. Rescue medication will be re-dispensed on Day 5 (V3), if necessary.

Subjects will be instructed to take only the rescue medication provided for pain in the ankle or any other pain (e.g., headache) or fever (e.g., due to common cold) they might experience during the trial. One tablet may be taken, repeated after at least 4 hours, if needed, up to a maximum of 2000 mg (four tablets) per day. No rescue medication is allowed within 6 hours prior to the study visits or within 12 hours of Study Visit 3.

The subject will receive a Subject Diary at Visit 1, Visit 2, and Visit 3 to record the information described in Section 6.8. At each visit, the investigator or designee will review the rescue medication use recorded in the diary and will transfer the relevant information to the CRF. Empty packages and rescue medication not used will be returned to the investigator. The investigator or designee will then compare the packages vs. the subject's rescue medication form and any discrepancies will be noted in the CRF.

The investigator will further investigate any instances in which rescue medication was taken for reasons other than ankle sprain and complete the Adverse Event Form, if appropriate.

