  - Over all Compliance % = [sum of (actual # of application from each tube)/sum of (expected # of application from each tube)\*100]

Scheduled applications will include all scheduled applications through the day before the final visit. On day 1, the percentage of gel used will be calculated based on the possible number of administrations on that day. If only 3 were possible, then 100 % compliance on that day will be considered 3 applications.

- % of gel used relative to number of actual applications \* 2g will be derived as following -
  - Total weight of study medication used: The percent (%) of gel used will be computed relative to the actual number of application made from randomization through the final visit multiplied by 2 g.in two ways –
  - If replacement kit number and replacement date (CRF: Study Medication Replacement) are missing then
  - Expected weight of study medication used from tube k= (number of applications per day from tube k )\*2g \* Expected number of days gel to be applied from tube k
  - Actual weight of study medication used from tube k= [(Baseline weight of tube k (weight of tube k after last day of application ; k=1, 2, 3, 4

GlaxoSmithKline Consumer Healthcare Confidential Page 16 of 36

**Percent of total medication used** = (Actual weight of medication used/Expected weight of medication used)\*100

In case there is repeated usage of single tube in a day then the over usage of the medication will be reflected in weight compliance.

- Compliance category: Compliance category will be defined in the following way -
  - Good: > 80% of the gel has been applied and > 80% of scheduled applications made,
  - Moderate: not Good and not Poor
  - Poor: < 50% of the gel has been applied or < 50% of scheduled applications made.

For subjects applying active gel only twice per day (DDEA 2.32%), an additional compliance computation will be performed relative to the tubes and applications of active gel. If a subject is falls into good compliance category in both (separately for the active gel and also combined with placebo) then that subject will be included in the PP protocol population.

For each subjects time of the first application, application of the study drug each time point each day and the weight of the four tubes on Day 1, 3, 5 and 8 will be listed in **PPD** :

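### Time to first rescue use is counted in whole calendar days although clock times are recorded, which costs resolution and, if rescue use is early and common, some power

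*SAP*

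**What the plan says.** SAP 4.4.3 replaces the protocol's rescue comparison (tablets and days, stratified by center, with Hodges-Lehmann intervals; Protocol 12.2.6) with time to first use. SAP section 5 confirms that the Hodges-Lehmann analysis is dropped, and SAP 4.6.1 lists no other rescue test, so this is the only between-arm rescue test the SAP keeps.

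The Censoring Rule gives the event time: "time will be derived as follows: Date of First Occurrence of Event- Date of Randomization + 1". For subjects without rescue use, "time will be derived as follows: Last Available Date in the study - Date of Randomization + 1".

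Clock times are collected:
- SAP 4.4.3 lists among the CRF items "Time (RMSTTM) and date (RMSTDTC) of rescue medication", as two separate variables.
- Protocol 6.8 has the diary record "Time and date of rescue medication" for each rescue dose. For the gel, "Every time gel is applied, the subject must document the time and date of application", and this includes the dose applied at the clinic.
- SAP 4.4.1 lists the time of first application for each subject.

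Rescue can be used from the first day: "The investigator will provide rescue medication (paracetamol, 500 mg tablets) to the subject at the baseline visit" (Protocol 6.10). SAP section 5 justifies the change only by saying that rescue use can be clearly analysed as time-to-event data. It gives no reason for working in days.

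**The concern.** A date minus a date plus 1 can only be 1, 2, 3 and so on, and treatment lasts 7 days, so there are very few distinct event times. Every first use before midnight on the randomization date takes the single value 1. Subjects enrol at different hours, so that first calendar day also differs in length from one subject to the next, and a later first use can be ranked as the earlier one.

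At stake is how much the one retained rescue comparison can show. The Kaplan-Meier curve has a single step for the whole randomization date, two arms with different medians on that date both print 1, and the log-rank test discards ordering information that the diary has captured.

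**Working it through.** **Plan's own figure.** None is stated for rescue use. The only design figure concerns the primary endpoint, and this point does not depend on it. It does reproduce: n per arm = 2 × 22² × (1.960 + 0.842)² / (13 − 5)² ≈ 119, against 120 stated.

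**Step 1: the rule applied to clock times.** With r the clock hour of randomization and e the hours elapsed to first use, the SAP value is floor((r + e)/24) + 1.

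| Randomized | First rescue | Elapsed | SAP value |
|---|---|---|---|
| 08:00 | 09:00 same day | 1 h | floor(9/24) + 1 = 1 |
| 08:00 | 23:00 same day | 15 h | floor(23/24) + 1 = 1 |
| 20:00 | 01:00 next day | 5 h | floor(25/24) + 1 = 2 |

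The first two subjects tie although 14 h apart. The third used rescue 10 h sooner than the second but is ranked later. A value of 1 covers up to 24 − 8 = 16 h for enrolment at 08:00, but only up to 24 − 20 = 4 h for enrolment at 20:00. In hours the three cases are distinct and correctly ordered: 1, 5, 15. This step needs no assumption about usage.

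**Step 2: how often it matters.** The documents give no rescue rate or timing, so this step rests on assumptions: 150 subjects per arm (from the planned 300), randomization hour uniform over 08:00-20:00, exponential time to first use, test-arm times 1.5 times longer, follow-up 168 h, 200 replicates. If all subjects use rescue:

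| Control median | First uses on randomization date | Pairs of users tied | Tied pairs more than 6 h apart | Pairs reversed | Power, hours | Power, days |
|---|---|---|---|---|---|---|
| 4 h | 73% | 60% | 21% | 1.6% | 93% | 80% |
| 8 h | 50% | 42% | 37% | 1.6% | 93% | 87% |
| 24 h | 22% | 22% | 53% | 0.7% | 90.5% | 89.5% |
| 48 h | 13% | 16% | 56% | 0.4% | 87% | 86.5% |

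The simulation standard error at 80% power is √(0.8 × 0.2/200) = 2.8 points. A repeat of the 4 h versus 6 h case gave 94% in hours against 79% in days. Over all scenarios run, including 30% and 60% users, 0.4-1.7% of pairs were reversed. With 30% or 60% users, power in days was within 2 points of power in hours, but power itself was low (5-29% in hours), so there was little to lose.

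**Step 3: other shapes of difference, same enrolment assumption.**
- 80% users, medians among users 12 h versus 24 h: 60% in hours, 47% in days.
- 40% versus 55% ever using rescue, same 12 h median: about 70-72% on either scale.
- No difference between arms: rejection 5.8% in hours, 5.5% in days.

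**The case against.** The strongest case against is that this is a refinement of a supplementary analysis. Time to first rescue use is not a protocol endpoint; those are tablets and days of use. It carries no power claim, and the primary conclusion does not depend on it. Early pain is compared elsewhere, through SPID and TOTPAR over 0-24 h, built on 2-hourly ratings on Day 1. The clock times will be listed and summarized even if the test ignores them. All of this stands and limits the weight of the point. It does not remove it, because the recorded times would make the retained test more informative at almost no cost.

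A reader might infer more than the documents support, in three ways.

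- *That the test is invalid or favors one arm.* The coarsening is the same in both arms, log-rank handles ties, and the null rejection rates above are near 5% on both scales.
- *That a large power loss is established.* One can construct it: with 80% users and medians among users of 3 h versus 6 h, power is about 55% in hours against 21% in days. That needs common, very early use and an early separation of the arms. If the arms separate only after 3 h, the figures are 11% and 9%.
- *That early use is where a twice-daily and a four-times-daily gel should differ.* Under Protocol 6.2 every subject's first dose comes from the morning tube, which holds active gel in both arms (Table 4-1), and doses on Day 1 are at least 3 h apart. In the protocol's own 15:00 example the second dose is also active in both arms. Application frequency therefore cannot separate the arms in the first hours. A formulation effect could, but the documents do not argue for one.

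It can also be said that the SAS code is not shown and the unit is not named. The plus 1 and the separate time variable leave a day count as the only natural reading.

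**Conclusion.** The point holds as a loss of resolution in a supplementary analysis. Ties, occasional reversals and the single step on the randomization date follow directly from the Censoring Rule. Ties are the main loss. Reversals need a first use after midnight in a subject enrolled later in the day, and affect about 0.4-1.7% of pairs under the assumed scenarios.

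The effect on power is conditional. It is material only if rescue use is early and common (about 94% against 79% for 4 h versus 6 h with all subjects using rescue). It is close to nil if use is late or rare, or if the arms differ only in the proportion using rescue. Small loss cannot be assumed just because hazards are proportional: the 94% against 79% case is itself a proportional-hazards case. All power figures rest on assumed usage rates, assumed enrolment hours and exponential times, so they illustrate a range and do not predict this trial's result. The primary non-inferiority conclusion is unaffected.

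**What to change.** Amend the Censoring Rule in SAP 4.4.3 before unblinding:

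1. Define event time in hours as the date and time of first rescue use (RMSTDTC with RMSTTM) minus the date and time of the first gel application. That origin is recorded for every subject, whereas no clock time of randomization is listed.
2. Put censoring on the same clock. The sources named in the rule are dates only, so state a convention, for example the end of that date.
3. State a rule for a missing clock time of rescue use, for example the midpoint of the interval possible on that date.
4. Run Kaplan-Meier and log-rank on hours, and report medians in hours.

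The cost is SAP wording and minor programming, with no new data. The downside is that some clock times will be imputed. How many cannot be known from the documents, because the diary is completed by the subjects themselves, so the number should be reported.
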